8.1 Power

We have estimated a loss to follow-up rate of approximately 25%, i.e., ~120 of the 162 participants will finish the entire protocol. Fall rates will be compared between each exercise intervention group and the control group with the use of negative binomial regression models. Despite mixed results with exercise interventions, two RCTs have shown that in-person exercise programs reduced fall rates (61% reduction in fall rate, Morris et al., 2015; 67% reduction in fall rate, Li et al., 2012) in patients with PD. We conducted an analysis of statistical

power using the PASS program to determine the sample size needed to detect a reduction in fall rate as low as 45%. A total of 40 participants per group will be required to provide 95% power to detect a between-group difference in fall rate of 45% for a specific exercise group vs. the control group (the group receiving the in-person program vs. the control group and the group receiving the remotely-delivered program vs. the control group), each at a two-sided significance level of 0.05. We assumed the control group rate of falls would be 1.3 falls per person month (Morris et al., 2015).

9. References

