STUDY PROTOCOL

Principal Investigator: [name]

[contact]

E-mail: [contact]

ClinicalTrials.gov number: NCT03972969

Protocol date: 3/16/2022

1. Aims/Objectives

A meta-analysis indicates that falls are very common in Parkinson's disease (PD), even within a brief period of 3 months, when about half of patients will sustain at least 1 fall (Pickering et al., 2007). Randomized, controlled trials (RCT) have examined the effects of exercise interventions on reducing falls in this population; however, with mixed results. The goal of the proposed research is to evaluate two approaches to implementing an exercise program: 1) an in-person exercise program that demonstrated a significant decline in fall rates over time in a small sample of patients (Sparrow et al., 2016) and 2) a home-based program centered around remote, exercise instruction.

In the proposed RCT, 162 VA patients with PD will be randomly assigned to one of three 3-month interventions: in-person exercise, remotely-delivered exercise, or health education. Fall rates will be compared between each exercise intervention group and the health education group.

2. Background Information

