2.1 Clinical Manifestations of Parkinson's Disease

PD is a progressive neurodegenerative disorder, characterized by insidious onset. The first signs become clinically manifested when about 70-80% of the dopamine producing cells of the substantia nigra have degenerated (Booij et al., 2001). The cardinal clinical manifestations of PD include resting tremor, rigidity, bradykinesia, and postural instability/gait disturbance (Olanow et al., 2009). Falls are one of the most serious complications of gait disturbances and postural instability in people with PD. People living in the community with PD fall frequently, with 60% falling annually and two-thirds of these falling recurrently (Latt et al., 2009; Allen et al., 2013; Bloem et al., 2001). These fall rates are double those in the general older population (Bloem et al., 2001), and contribute to inactivity, restrictions in mobility, fear of falling, and greater disability (Allen et al., 2010; Wielinski et al., 2005).

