Patients with PD will be identified from the VA Boston Healthcare System (Boston, West Roxbury, and Brockton VA medical centers and their five satellite clinics) and the Bedford VA Medical Center and its four satellite clinics with the use of the Corporate Data Warehouse (CDW). Specifically, this approach will involve searching the CDW to identify patients who are 40 years of age or older with an ICD code for PD and a prescription for a dopaminergic medication. To assess electronic medical records we will use the CAPRI system, which provides one interface into the VISTA systems within VISN 1. Patients with PD typically have an initial Neurology consultation and then are seen in Neurology Clinic every 6 months. A standardized VA note format is utilized which includes HPI, medications, and detailed neurologic examination at each visit. The initial VA Neurology consultation will be reviewed with as many subsequent clinic notes as needed to establish the diagnosis of PD and responsiveness to dopaminergic therapy. The two most recent Neurology Clinic notes will also be reviewed to determine current medication use and functional status. Pharmacy records will also be reviewed to confirm stability of medication dosage. Also, Primary Care provider notes and any hospital discharge summaries from the previous year will be reviewed for evidence of exclusionary conditions.

b. Subject Inclusion Criteria

Patients with PD who meet eligibility criteria will be recruited into this study. Specific inclusion criteria will include a physician diagnosis of idiopathic PD; at least 2 of the 3 cardinal signs of PD (resting tremor, rigidity, bradykinesia); response to dopaminergic medication; and an age of 40 years or older.

c. Subject Exclusion Criteria

Specific exclusion criteria will include a diagnosis of angina pectoris (unless symptomatically resolved post-revascularization); a history of myocardial infarction (MI) within 6 months; and a history of ventricular dysrhythmia requiring current therapy.

7. Data Collection and Management

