7.1 Falls Assessment

The rate of falls will be assessed prospectively. The collection of detailed and prospective information about falls follows the recommendations of the Prevention of Falls Network Europe consensus statement (Lamb et al., 2005) and a Cochrane Collaborative review (Gillespie et al., 2012). A fall is defined as an unexpected event in which a participant comes to rest on the ground, floor, or lower level. A near fall is defined as an occasion in which a participant felt that he was going to fall but did not actually do so. Participants will be asked to record falls as they occur on monthly calendars supplied by the investigators. Also, they will be asked to record the circumstances surrounding a fall or near fall (i.e., location, time of day, direction of fall, activity being performed, presence of an environmental trigger, injuries sustained, and medical attention received).

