where FALLS_i is the number of falls for the ith participant over 3 months, t_i is the person-months of follow-up between the baseline exam and the 3-month exam for the ith participant, IN_PERSON and REMOTE are two dummy variables indicating that the patient was randomized to receive the in-person intervention (IN_PERSON=1, REMOTE=0), to receive the remotely-delivered intervention (IN_PERSON=0, REMOTE=1), or to the control group (IN_PERSON=0, REMOTE=0), and CONFOUNDER is a mean-centered hypothetical confounding variable. In the above model we will include an offset for the time between baseline and follow-up, which may vary slightly around the 3-month target date. **Coefficient a** estimates the log(rate of falls per month) for a control participant. The incidence rate ratio (IRR) in falls per month for a participant in the in-person exercise group vs. a participant in the control group with the same level of confounders is estimated by exp(b1). The IRR in falls per month for a participant in the remotely-delivered exercise group vs. a participant in the control group is estimated by exp(b2).

To compare the fall rates between groups, the coefficients of interest are b1 and b2. **Coefficient b1** will be tested to compare the in-person intervention vs. the control group and **coefficient b2** will be tested to compare the remotely-delivered intervention vs. the control group. Furthermore, the linear contrast b1-b2 will be tested to compare the fall rates between the in-person intervention and the remotely-delivered intervention. Specifically, exp(b1-b2) is the estimated IRR in falls per month between the in-person and remote groups.

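### The 95% power in section 8.1 rests on an unstated dispersion; in an unadjusted negative binomial it needs roughly nine in ten controls to fall within 3 months, where the protocol says about half.

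*Combined protocol and SAP*

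**What the plan says.** Section 8.1 states "A total of 40 participants per group will be required to provide 95% power to detect a between-group difference in fall rate of 45" per cent, for each exercise arm against control, at a two-sided 0.05 level. It adds "We assumed the control group rate of falls would be 1.3 falls per person month" and allows for about 25% loss, so that about "120 of the 162 participants will finish the entire protocol". The software is named (PASS) and the analysis is negative binomial regression. No dispersion parameter is given.

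Section 8 counts falls over 3 months with an offset for follow-up time. The model has one covariate term, described only in general: "CONFOUNDER is a mean-centered hypothetical confounding variable".

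Elsewhere the protocol describes how many patients fall. Section 1: "even within a brief period of 3 months, when about half of patients will sustain at least 1 fall". Section 2.1: "with 60% falling annually and two-thirds of these falling recurrently". Eligibility in section 6(b) starts "Specific inclusion criteria will include a physician diagnosis of idiopathic PD; at least 2 of the 3 cardinal signs of PD" and goes on to drug response and age; the exclusions in 6(c) are cardiac. Neither asks for a history of falls. On measurement, section 7.1 says "The rate of falls will be assessed prospectively"; it describes no collection of falls before baseline.

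**The concern.** In a negative binomial model the variance of the log rate ratio has two parts: one that shrinks as the fall rate rises, and one, proportional to k, that does not. A power figure that omits k cannot be reproduced or judged.

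The rate and k together also fix the share of people who fall at least once, so the missing value can be compared with the protocol's own figures on fallers. If the k needed for 95% implies a share far from those figures, then the rate, the k or both do not fit them.

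The 95% is the document's only statement of how likely the trial is to detect a 45% reduction. After a null result, readers would lean on it as evidence against an effect of that size.

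**Working it through.** **Inputs.** From section 8.1: n = 40 per group, rate ratio 0.55, two-sided 0.05, 1.3 falls per month. From section 8: 3 months of counting. Expected falls are therefore mu0 = 3 × 1.3 = 3.9 in controls and mu1 = 0.55 × 3.9 = 2.145 with exercise; |ln 0.55| = 0.598. No covariate is assumed.

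**Formulas.**
- V1 = 1/mu0 + 1/mu1 + 2k.
- Power = Φ[(√n × 0.598 − 1.96 √V0) / √V1].
- V0 is the variance used under the null. Three common choices are V1 itself (Wald), 4/(mu0 + mu1) + 2k (pooled rate) and 2/mu0 + 2k (reference rate).
- Share with at least one fall = 1 − (1 + k·mu)^(−1/k), or 1 − e^(−mu) when k = 0.

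**Can the 95% be reproduced?** Not from the stated inputs, because k is missing. With k = 0 (Poisson), 22 to 27 per group would suffice and 40 would give 99.4 to 99.7%, so the 40 is not a Poisson figure. Solving for k by Wald:
- the required standard error is 0.598/(1.960 + 1.645) = 0.1658;
- V1 must be 40 × 0.1658² = 1.100;
- 1/3.9 + 1/2.145 = 0.723, so k = (1.100 − 0.723)/2 = 0.189.

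The pooled and reference formulas give k = 0.205 and 0.247.

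**What that k implies.** Wald: 1 − (1 + 0.189 × 3.9)^(−1/0.189) = 94.6% of controls falling in 3 months. The other two formulas give 94.3% and 93.5%. Over 12 months with constant individual rates, all three exceed 99%.

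**Could another rate rescue it?** Over all pairs of rate and k that give 95% at 40 per group, the share of fallers is smallest at k = 0. By Wald, 2.818/mu0 = 1.100 gives mu0 = 2.56 (0.85 per month) and 1 − e^(−2.56) = 92.3%. Pooled gives 91.3% (0.81 per month) and reference 88.3% (0.71 per month).

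**Power at the protocol's proportions of fallers.** If half fall in 3 months, mu0 = (2^k − 1)/k. At 1.3 per month this gives k = 4.08, V1 = 0.723 + 8.16 = 8.88 and standard error √(8.88/40) = 0.471, so power = Φ(0.598/0.471 − 1.96) = 25%. Wald figures; the last column is an upper bound if all 162/3 = 54 per group gave full data:

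| Controls | k | Falls/month | Power, n = 40 | n = 54 |
|---|---|---|---|---|
| Half fall in 3 months | 4.08 | 1.3 | 25% | 31% |
| Half fall in 3 months | 1 | 0.33 | 41% | 52% |
| Half fall in 3 months | 0.19 | 0.25 | 46% | 57% |
| Half fall, best over all rates | 0 | 0.23 | 47% | 59% |
| 60% fall in 12 months, best over all rates | – | – | 26% | 34% |

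The most favourable formula raises the last two rows to 59% (70%) and 31% (39%).

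**Power at 1.3 per month across k** (Wald, n = 40):

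| k | Controls falling in 3 months | Power |
|---|---|---|
| 0.2 | 94% | 95% |
| 0.5 | 89% | 82% |
| 1 | 80% | 63% |
| 2 | 66% | 41% |
| 4 | about half | 25% |

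**Simulation.** Three-arm negative binomial fits with model-based errors, 2,000 trials per setting, n = 40, agree. At 1.3 per month: 95.6% at k = 0.19, 81.2% at 0.5, 62.9% at 1, 40.6% at 2 and 26.5% at 4.08. With half falling and k = 0: 45.8%.

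**Sensitivity.** The smallest share of fallers compatible with 95% is 84 to 88% for a one-sided 0.05 test, and 80 to 85% if all 54 per group gave full data. Counting 6 months at 1.3 per month still implies about 91% falling in 3 months.

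**The case against.** **The proportions are background, not design assumptions.** They describe people with Parkinson's disease in general and come from other cited sources than the 1.3 per month. This is true, and a sample at higher risk may be intended. But they are the protocol's only figures on the share falling, the half opens its statement of aims, and nothing in eligibility selects fallers. The request is to say which figure will not hold.

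**The background figures do not fit one another.** Reading recurrent as two or more falls a year, 60% falling with two-thirds of them recurrent gives k of about 1.49 and 0.16 falls per month, hence about 31% falling in 3 months, not half. This stands as a warning against precision. It does not help the 95%: power at that fit is again about 25%.

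**The planned model is adjusted.** This is the strongest point. Suppose half of patients never fall, the rest share one Poisson rate, and the covariate separates them perfectly. The variance is then (1/7.8 + 1/4.29)/20 = 0.018 and power is 99%. So the bounds above apply only without a covariate. But the plan names none, describes only prospective recording of falls, and puts no figure on adjustment in section 8.1.

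**The size depends on the model.** This is also true. If half of each arm has no falls and every other control has exactly 7.8, the variance is 2/40 and power is 76% (87% with 54 per group). That needs robust standard errors, which the SAP does not name; with model-based errors it simulates at 34% (52%).

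**Conclusion.** The concern holds. Section 8.1 omits the input that drives its power figure. In the unadjusted negative binomial model with a common k, 95% at 40 per group needs at least 88 to 92% of controls to fall within 3 months at any rate, and 93 to 95% at the stated 1.3 per month. That does not fit about half in 3 months or 60% in a year.

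With half of controls falling, power is 25% at the stated rate and no more than 47% at any rate (59% by the most favourable formula), roughly half the stated figure or less on the Wald calculation.

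The missing k and the mismatch are firm. The size of the shortfall is not: it depends on the shape of the fall distribution and on any covariate. Because the PASS output is not shown, this is not a claim that the software was misused.

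**What to change.** Keep the sample size and change the text of section 8.1.

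1. State the k used in the PASS calculation and its source. If adjustment was credited, name the covariate and its assumed effect.
2. Reconcile k and the 1.3 falls per month with the proportions of fallers in sections 1 and 2.1, and say which of them is not expected to hold in this trial.
3. Replace the single 95% with a range, for example:

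> With 40 completers per group, 1.3 falls per person-month in controls, two-sided 0.05 and no covariate adjustment, power for a 45% reduction is about 95% if k = 0.2 (94% of controls falling in 3 months), 82% if k = 0.5 (89%), 63% if k = 1 (80%), 41% if k = 2 (66%) and 25% if k = 4 (about half).

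If the rate is what is revised, give the same range at the revised rate.

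The cost is protocol wording only, with no additional patients. The downside is that a single favourable figure becomes a less favourable range.

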7.2 Data Management and Security

For the purposes of this study, each patient will be assigned a unique randomly generated ID number, which will be used on all electronic data stored locally. A walk across file will be maintained to link the patient

with the random ID number and will be encrypted and stored in a separate location from all other data extracted. Only the study coordinator and PI will have access permissions to this file.

All electronic databases related to this protocol will be stored locally on a VA server in an entry controlled, locked room at the Jamaica Plain campus of the VA Boston Healthcare System. There are multiple levels of security to ensure the integrity and confidentiality of all data. The computer system operates entirely within the VA network, which is protected by a firewall maintained by the VA Office of Information Technology. Part of the maintenance of the VA server is that it is backed up regularly; therefore, all data related to this protocol will be routinely backed up and stored behind the VA firewall. Only authorized users can log on to the server. An additional layer of restrictions is at the file and directory level. Users can only access portions of the data to which they are entitled. Access to all data on the server is password protected.

All paper forms will be secured in a locked fireproof study cabinet. Only the PI will have keys to the study cabinet. All data will be kept indefinitely or until the law allows their destruction in accordance with the VA Record Control Schedule.

To minimize data entry errors, all data collected on paper forms will be entered twice by a trained staff member using software that allows specification of valid responses for each entry field. Upon second entry of each record, the software will analyze each field to check for discrepancies in the two entries. Entry errors will be corrected on the spot and any errors requiring more extensive review will be deleted and re-keyed after the errors are resolved.

8. Statistical Analysis Plan

The rate of falls over 3 months will be compared between each intervention group and the control group and between the two intervention groups, with the use of negative binomial regression models. We will base our analyses on the following model

$$\log \left[\frac{E(FALLS_i)}{t_i} \right] = a + b1.IN_PERSON + b2.REMOTE + c.CONFOUNDER \quad (1)$$

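### Do the three pairwise fall-rate comparisons need a multiplicity adjustment?

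*Combined protocol and SAP*

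**What the plan says.** Section 8 opens by saying that three-month fall rates "will be compared between each intervention group and the control group and between the two intervention groups". All three comparisons come from model (1):

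- coefficient b1 "will be tested to compare the in-person intervention vs. the control group";
- coefficient b2 "will be tested to compare the remotely-delivered intervention vs. the control group";
- in addition, "the linear contrast b1-b2 will be tested to compare the fall rates between the in-person intervention and the remotely-delivered intervention".

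The three do not have equal standing. Section 8 states that "the coefficients of interest are b1 and b2". The aims in Section 1 name only the control comparisons: "Fall rates will be compared between each exercise intervention group and the health education group". Section 8.1 also sizes the trial for those two alone: "A total of 40 participants per group will be required to provide 95% power" for a 45% lower fall rate in a given exercise group than in control, "each at a two-sided significance level of 0.05". No significance level is given for b1-b2.

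The plan does not rank b1 against b2. It contains no multiplicity adjustment, global test, testing order or overall success rule.

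**The concern.** The two programs are closely related. Both draw on the same balance framework, list the same types of exercise, and are judged on the same outcome over the same three months against one control group of about 40 completers. If that control group happens to have an unusually high fall rate, both programs look better at once. A reader who treats a significant result in either arm as evidence that exercise reduces falls is applying a rule whose false-positive rate is nearly twice 5%. Section 2.3 describes the existing evidence as mixed, so a spurious positive would matter. The apparent remedy also looks nearly free: one sentence in the plan and one more test from the same fitted model.

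**Working it through.** **Inputs.** Two-sided 0.05 for each control comparison, 40 per group, control rate 1.3 falls per person-month and rate ratio 1 − 0.45 = 0.55 (Section 8.1); three months of counting (Section 8); 162 randomized to three arms (Section 1). Assumed, because not stated: 1:1:1 allocation, level 0.05 for b1-b2, and the negative binomial dispersion k.

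**1. The plan's sample size.** Dropout: 40 / (1 − 0.25) = 53.3, so 54 per arm and 3 × 54 = 162, as stated. For power, the variance of the log rate ratio with n per group is

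[1/(1.3 × 3) + 1/(0.715 × 3) + 2k] / n = (0.7226 + 2k) / 40.

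The effect is |ln 0.55| = 0.598, and power is Φ(0.598/SE − 1.96). With k = 0.189, SE = √(1.1006/40) = 0.166 and power = Φ(3.604 − 1.96) = 95.0%. Other choices of null variance give 95% at k up to about 0.25. The stated power can be neither confirmed nor refuted, because no dispersion is given. The error rates in step 2 do not depend on k.

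**2. Chance of at least one false positive when neither program works.** With equal arms and a shared control, the two test statistics have correlation 0.5.

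- Two control tests: 0.05 + 0.05 − P(both significant) = 0.10 − 0.0093 = 9.07%. Independent tests would give 1 − 0.95² = 9.75%. The shared control therefore lowers this rate slightly, and it leaves each test's own 5% unchanged.
- All three tests at 0.05: the studentized range for three groups, evaluated at 1.96 × √2 = 2.772, gives 12.2%.
- False claims of benefit only, two control tests: 4.5%, against 2.5% for one test.

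These are large-sample figures. In simulations of negative binomial Wald tests at 40 per arm, with k from 0.19 to 4.1, the two-test rate was 9.7% to 11.4%. The excess over 9.1% is small-sample bias of the Wald test, not multiplicity: a single such test rejected 5.6% to 6.2% of the time.

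**3. What an adjustment would do.** The cheapest option is to test b1 = b2 = 0 on 2 df at 0.05 and go on to the pairwise tests at 0.05 only if that is significant. With exactly three groups this is a closed procedure. Under normal theory the error over all three tests falls to 5.0%. With negative binomial Wald tests at 40 per arm, simulations put it between 5.4% and 7.4%.

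Power of one control comparison at 40 per group, rate ratio 0.55, both programs effective:

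| k | no gate | with gate |
|---|---|---|
| 0.19 | 95.0% | 94.3% |
| 0.5 | 82% | 79% |
| 1 | 63% | 56% |
| 2 | 41% | 33% |

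If only one program works, the gated figure at k = 0.19 is about 93.5%. At that dispersion, Bonferroni over the two control tests (0.025 each) gives about 91%, or needs 47 per group for 95%. A Dunnett-type level (0.027 each) gives about 92%, or needs 46 per group.

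**The case for a change.** The best case for a change is that these are two deliveries of one type of exercise, not unrelated treatments, so treating them as separate questions is less convincing than usual. The plan records no reason for leaving the tests unadjusted. The gate keeps every 0.05 level already written down, costs less than 1 point of power at the plan's own assumptions when both programs work, and could be added before analysis.

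Much of this stands. The error rates are right, the programs are related, and the gate is a valid procedure. A sentence giving the sponsor's position would be helpful, but its absence is missing detail and does not make the planned tests wrong.

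The rest does not carry. The harm depends on an either-program success claim, and the documents make none: Section 1 describes two approaches to be evaluated, and Section 8 gives each its own coefficient and rate ratio. Comparing 9% with the stated 5% sets a familywise rate against a per-comparison one. The small power cost relies on a dispersion solved backwards from the stated power; if falls are more variable, the cost is several points. The gate also makes the result for one program depend on what happens in the other arm.

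**Conclusion.** No change follows; this is a fair trade-off. The plan tests two distinct modes of delivery, in person and by smartphone at home, each against control at its own 0.05. Reporting both rate ratios with their unadjusted tests is a defensible convention for such a design. The relevant familywise figure is about 9%, since the aims, the named coefficients and the power calculation all centre on the two control comparisons. The 12% figure also needs a 0.05 level for b1-b2 that the plan does not state. Both figures assume equal arms, no effect of either program, and large-sample normal tests.

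Gating would bring the error close to 5%. With both programs effective it would cost about 1 point of power at k near 0.19, 3 at k = 0.5, 7 at k = 1 and 8 at k = 2. Since the documents give no dispersion, the size of that cost is unknown. Accepting it is a choice open to the sponsor, not the correction of an error. Readers can judge the results properly as long as all three comparisons are reported and a finding for one program is not presented as a finding for exercise in general.
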